### 10.2.1 Accrual Ceiling

It is expected that 10 evaluable participants can be accrued within 1 year.

The accrual ceiling will be set at 16 participants to account for the 4 participants treated in Cohort 1, Arm 1 (VIPOR-Nivo; closed) in addition to the 10 participants required to assess success in Cohort 1, Arm 2 (VIPOR), and to also allow for 2 inevaluable participants.

## 10.3 POPULATIONS FOR ANALYSES

Any participants who received at least one dose of any study drugs will be evaluated for success.

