### Study Design:

- A safety study of 10 evaluable participants with PCNSL or SCNSL treated with VIPOR (the original study protocol enrolled 4 participants to Cohort 1, Arm 1 consisting of VIPOR plus nivolumab which is now closed).
- Participants will receive VIPOR in 21-day cycles for a maximum of 6 cycles to collect data on safety and efficacy.
- Accrual ceiling will be set at 16 participants to allow for a few inevaluable participants or screen failures.

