## 10.2 SAMPLE SIZE DETERMINATION

In participants with CNS lymphoma, it would be desirable if the success rate were consistent with 80% or better as opposed to 50%. To do so, the following design will be used. In this small pilot trial, 10 evaluable participants who receive VIPOR will be evaluated for the feasibility of achieving success. If there are 7 or more who exhibited a success, the probability of this occurring is no more than 17.2% if the true probability of success is 50% or less and is at least 87.9% if the true probability of success is 80% or more. Thus, attaining success in 7 or more treated participants would be considered enough to demonstrate an adequate level of safety and feasibility for the treatment based on the specified criterion.

As of 6/6/2022, four total participants were enrolled and treated on Cohort 1, Arm 1 (i.e., VIPOR-Nivo). These participants will not be included in the analysis of the primary endpoint but will be evaluated for toxicity and survival outcomes.

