### 10.3.2 Evaluable for objective response:

Only those participants who have measurable or evaluable disease present at baseline, have received at least one cycle of VIPOR, and have had their disease re-evaluated will be considered evaluable for response. These participants will have their response classified according to the definitions in Section 6.3. (NOTE: Participants who exhibit objective disease progression prior to the end of cycle 1 will also be considered evaluable.)

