## 10.4 STATISTICAL ANALYSES

### 10.4.1 General Approach

Participants will be evaluated to see if they are successful with respect to feasibility and safety.

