#### 10.4.2 Analysis of the Primary Endpoints

Success is defined as completing at least 2 cycles of VIPOR therapy without the need to discontinue treatment due to toxicity. The fraction of participants who achieve a success will be determined and reported along with a 95% confidence interval.

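### Does the 7-of-10 rule leave open how early stops without toxicity and inevaluable participants are counted?

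*Combined protocol and SAP*

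**What the plan says.** All references are to the combined protocol and SAP.

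- **Endpoint.** Section 10.4.2: "Success is defined as completing at least 2 cycles of VIPOR therapy without the need to discontinue treatment due to toxicity". The endpoint column of section 10.1 says the same in other words.
- **Population.** Section 10.3: "Any participants who received at least one dose of any study drugs will be evaluated for success". Section 10.2 removes the four Arm 1 participants from the primary analysis.
- **Decision rule.** Section 10.2: "10 evaluable participants who receive VIPOR will be evaluated for the feasibility of achieving success". It then says that "attaining success in 7 or more treated participants would be considered enough to demonstrate an adequate level of safety and feasibility". The stated chance of passing is at most 17.2% if the true success rate is 50% or less, and at least 87.9% if it is 80% or more.
- **Ceiling.** Section 10.2.1 builds 16 from the four closed-arm participants plus "the 10 participants required to assess success in Cohort 1, Arm 2 (VIPOR), and to also allow for 2 inevaluable participants". The précis gives the purpose of the ceiling as "to allow for a few inevaluable participants or screen failures".
- **Purpose.** Section 10.4.1: "Participants will be evaluated to see if they are successful with respect to feasibility and safety". Section 10.1 also pairs safety with feasibility, whereas section 1.1.1 and the précis pair safety with tolerability.

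**The concern.** Two things seem to be missing.

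First, toxicity is the only reason for stopping that the success definition names. Section 3.8.1 lists others, such as progression, participant request and investigator's discretion, and any of them could occur before cycle 2 ends. For the response endpoint, section 10.3.2 deals with early progression expressly: "Participants who exhibit objective disease progression prior to the end of cycle 1 will also be considered evaluable". Success has no matching sentence.

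Second, if one dose is enough to be evaluated, it is not obvious who the two inevaluable participants could be, or which denominator applies if more than ten are dosed.

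In an open-label study of ten with a single decision rule, one or two classifications can settle the result. Four early progressions and no toxicity stop give 6/10, so the rule is not met, although 10/10 were free of a toxicity stop (exact 95% CI 69.2% to 100%). Three toxicity stops and seven completions give 7/10, so the rule is met (34.8% to 93.3%). If the counting were decided after the outcomes were known, the rule would lose its meaning.

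**Working it through.** **1. The plan's own figures.** Inputs from section 10.2: n = 10, cut-off 7, success rates 0.50 and 0.80. With X binomial:

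- P(X ≥ 7 | 10, 0.5) = (120 + 45 + 10 + 1)/1024 = 176/1024 = 17.2%.
- P(X ≥ 7 | 10, 0.8) = 0.2013 + 0.3020 + 0.2684 + 0.1074 = 0.8791, or 87.9%.

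Both reproduce.

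**2. Classifying an early stop.** Apply 10.3 and then 10.4.2 to a dosed Arm 2 participant:

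| Course | In population (10.3)? | Two cycles completed? | Result |
|---|---|---|---|
| Completes two cycles, no toxicity stop | yes | yes | success |
| Toxicity stop before the end of cycle 2 | yes | no | not a success |
| Progression, death or withdrawal before the end of cycle 2 | yes | no | not a success |

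No row is undetermined. The note in 10.3.2 is needed there because response evaluability otherwise requires a full cycle and a re-evaluation, which would drop early progressors. The success population requires one dose, so they are already in it.

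**3. Does disease course damage the stated figures?** Let t be the toxicity-free rate and d the rate of early non-toxicity stops, assumed independent of toxicity. The success rate is then S = t(1 − d). The documents give no value for d, so 5%, 10% and 20% are assumptions.

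| d | S if t = 0.80 | P(pass) | S if t = 0.50 | P(pass) | t needed for S = 0.80 |
|---|---|---|---|---|---|
| 5% | 0.76 | 79.9% | 0.475 | 13.4% | 0.842 |
| 10% | 0.72 | 70.2% | 0.45 | 10.2% | 0.889 |
| 20% | 0.64 | 48.7% | 0.40 | 5.5% | 1.000 |

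The third column looks like lost power, but it is evaluated at S below 0.80. Section 10.2 sets 50% and 80% for success, which is S. At S = 0.80 the chance of passing is 87.9% for any d. At t = 0.50 the chance of passing falls below 17.2%, so early non-toxicity stops make the rule stricter.

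**4. Denominator.** 4 + 10 + 2 = 16, which leaves 16 − 4 = 12 places in Arm 2. Section 10.2 speaks of ten who receive VIPOR and of treated participants, and 10.3 counts anyone with one dose, so evaluable means dosed and inevaluable means never dosed. Such participants exist in the plan: section 2.3.1 covers those who consent but are not assigned to the intervention, and section 3.8.2 covers loss of eligibility between enrolment and day 1. Only if 11 or 12 were dosed and the cut-off stayed at 7 would the error at 50% rise:

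- n = 11: 562/2048 = 27.4%.
- n = 12: 1586/4096 = 38.7%.

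**5. Would replacing early non-toxicity stops be better?** With 12 places and no claim made if fewer than ten are evaluable, a regimen with t = 0.80 passes with probability P(at least 10 of 12 evaluable) × 0.8791:

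- d = 5%: 0.9804 × 0.8791 = 86.2%.
- d = 10%: 0.8891 × 0.8791 = 78.2%.
- d = 20%: 0.5583 × 0.8791 = 49.1%.

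The gain over the third column above is 6.3, 8.0 and 0.4 points. The cost is reliance on open-label attribution. Suppose t = 0.50, d = 0, and 20% of toxicity stops are labelled as something else and replaced. The evaluable fraction is 0.5 + 0.5 × 0.8 = 0.9, and success among the evaluable is 0.5/0.9 = 0.556. The error is then 0.2779 × 0.8891 = 24.7%, against 17.2%.

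**The case for a change.** The best case for a change is that a favoured reading is not a stated rule. Evaluability is defined for toxicity and for response but not for the primary endpoint. The précis names inevaluable participants and screen failures as alternatives, which suggests that they are not the same people. There is no replacement rule, and the ceiling would physically allow 12 dosed in Arm 2. If an analyst treated early non-toxicity stops as non-failures, the success rate at t = 0.50 would become 0.5 × 0.9 + 0.1 = 0.55 with d = 10%, and the chance of passing 26.6%. With d = 20% it would become 0.60, and the chance 38.2%. Finally, the primary result alone would not show whether a failed rule reflected toxicity or lymphoma.

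Part of this stands. The meaning of inevaluable has to be inferred, and the objective is worded in two ways. The toxicity table in section 10.4.4 goes by grade and type and does not count toxicity-related stops as such.

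The rest does not carry. Counting a non-completer as anything but a non-success contradicts 10.1 and 10.4.2, so the 26.6% and 38.2% belong to a departure from the plan. A participant who is registered and then loses eligibility before day 1 is inevaluable without having failed screening in the sense of 2.3.1, so the précis wording fits the never-dosed reading. With ten participants, the reasons for early stops are easily set beside the primary result: section 3.8.1 supplies the categories, and section 2.3 requires a status update when someone leaves protocol therapy. Toxicity, response and progression-free survival are reported in any case.

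**Conclusion.** The concern does not call for a change. Followed as written, the plan gives one answer for every dosed participant and a 7-of-10 rule whose 17.2% and 87.9% are correct. Counting early non-toxicity stops as non-successes suits an endpoint tied to safety and feasibility, and it errs on the cautious side for participants. The price is that disease course can contribute to a failed rule. That is a fair trade-off, and replacing such participants would gain between 0.4 and 8.0 points of pass probability over the assumed 5% to 20% range while exposing the rule to attribution error. The difference between tolerability and feasibility is a slip of wording that alters neither the endpoint nor the rule.

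This rests on two readings: that inevaluable means never dosed, and that the rule is applied to ten dosed Arm 2 participants. Both fit sections 2.3.1, 3.8.2, 10.2, 10.2.1 and 10.3 and the précis. If more than ten were dosed in Arm 2, the analyst would need to hold the rule to the first ten, because 7 of 11 or 7 of 12 is a different test. The plan schedules no such enrolment.

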### 10.3.1 Evaluable for toxicity:

All participants will be evaluable for toxicity from the time of their first treatment with any of the VIPOR study drugs.

### 10.3.2 Evaluable for objective response:

Only those participants who have measurable or evaluable disease present at baseline, have received at least one cycle of VIPOR, and have had their disease re-evaluated will be considered evaluable for response. These participants will have their response classified according to the definitions in Section 6.3. (NOTE: Participants who exhibit objective disease progression prior to the end of cycle 1 will also be considered evaluable.)

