### 3.4.3 Additional Information

#### 3.4.3.1 Response Assessments

Participants will be restaged at the following time points. Response assessments will be done by investigators. For additional details on response criteria, see Section [6.3](#).

- After cycle 1 (within 7 days prior to treatment on day 1 of cycle 2)
- After cycle 3 (within 7 days prior to treatment on day 1 of cycle 4)
- After cycle 6 (cycle 6 day 21 +/- 7 days)

**NOTE:** If a participant stops treatment for any reason other than disease progression before completion of 6 cycles, response assessments should continue as listed in Study Calendar ([Appendix D](#)).

**NOTE:** Restaging scans should only be performed based on involved sites of disease at baseline (e.g., patients with CNS disease only should undergo restaging MRI brain and PET brain while those with systemic disease should also undergo CT C/A/P and PET torso).

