#### 3.4.3.2 Disease Progression

At the time of suspected or confirmed disease progression, the following are required:

- Imaging by MRI brain, CT scan, and FDG-PET (only if can be performed at NIH)
- Lumbar puncture/Ommaya tap for CSF studies including protein, glucose, cell count/differential, cytology, and flow cytometry
- Ophthalmologic evaluation (only if ocular involvement was noted at baseline evaluation)
- Symptom-guided clinical assessment with physical exam
- Lymphocyte phenotyping TBNK

**NOTE:** In the event that disease progression is not confirmed, yet a decision is made to initiate a new anti-cancer treatment for any reason, all of these assessments should be done prior to start of the new therapy.

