## 10 STATISTICAL CONSIDERATIONS

### 10.1 OBJECTIVES AND ENDPOINTS

OBJECTIVES	ENDPOINTS	JUSTIFICATION FOR ENDPOINTS
Primary		
To determine the safety and feasibility of VIPOR in primary DLBCL of the CNS (PCNSL) and secondary CNS lymphoma (SCNSL)	The fraction of participants who completed at least 2 cycles of VIPOR therapy without stopping due to toxicity.	Standard endpoint for cancer clinical trials.
Secondary		
To determine the overall response rate (ORR) of up to 6 cycles of VIPOR in CNSL	ORR = CR+PR- assessed after cycles 3 and 6	Standard endpoints for cancer clinical trials

OBJECTIVES	ENDPOINTS	JUSTIFICATION FOR ENDPOINTS
To determine the complete response (CR) rate of up to 6 cycles of VIPOR in CNSL	CR- The rate of complete response by Lugano, assessed after cycles 3 and 6	Standard endpoints for cancer clinical trials, CR is the endpoint chosen because with these diseases, PR is not relevant as all participants will relapse.
To determine the duration of response (DOR) after VIPOR in CNSL	Duration of response (DOR)- measured from the time of first response until the first date that recurrent or progressive disease is objectively documented, death, or, in the absence of PD, date of last assessment (10 years post-treatment)	Standard endpoints for cancer clinical trials, success of regimens will be determined by these endpoints.
To estimate the progression-free survival (PFS) after VIPOR in CNSL	Progression free survival (PFS) – calculated up to 10 years post-treatment	Standard endpoints for cancer clinical trials, success of regimens will be determined by these endpoints.
To assess overall survival (OS) after VIPOR in CNSL	Overall survival (OS)- calculated up to 10 years post-treatment	Standard endpoints for cancer clinical trials, success of regimens will be determined by these endpoints.
Tertiary/Exploratory		
To perform comprehensive molecular profiling of CNSL tumors and explore correlations with clinical response	Each of these will be evaluated using descriptive methods and reported as exploratory results. If any statistical tests are performed in these analyses, the results will be presented without adjustment for multiple comparisons but reported in the context of the number of tests performed. See Section 5.1 for collection timepoints.	Exploratory analysis
To genotype circulating tumor DNA (ctDNA) from plasma and CSF and correlate to tissue genotyping		
To study cytokine changes across VIPOR therapy		

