#### 10.4.3 Analysis of the Secondary Endpoints

The following secondary endpoints will be analyzed as described:

- The overall response rate (ORR) of up to 6 cycles of VIPOR in PCNSL and SCNSL will be reported along with a 95% confidence interval.
- The complete response (CR) rate of up to 6 cycles of VIPOR in PCNSL and SCNSL will be reported along with a 95% confidence interval.
- The duration of response (DOR) after VIPOR in PCNSL and SCNSL will be determined starting at the date a response is identified and will be estimated using a Kaplan-Meier curve along with a median DOR, and its associated 95% confidence interval.
- The progression-free survival (PFS) after VIPOR in PCNSL and SCNSL will be estimated using progression or death without progression as events, using a Kaplan-Meier curve. The median will be determined and presented with its associated 95% confidence interval.
- Overall survival (OS) after VIPOR in PCNSL and SCNSL will be determined using a Kaplan-Meier curve. The median will be determined and presented with its associated 95% confidence interval.

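### The response population in 10.3.2, the natural denominator for ORR and CR, drops dosed participants lost in cycle 1 without documented progression or never re-evaluated, instead of counting them as non-responders

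*Combined protocol and SAP*

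**What the plan says.** All references are to the combined protocol and SAP.

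- **Response population (10.3.2).** Participants need measurable or evaluable disease at baseline and must "have received at least one cycle of VIPOR, and have had their disease re-evaluated will be considered evaluable for response". The note adds one exception: "Participants who exhibit objective disease progression prior to the end of cycle 1 will also be considered evaluable". Section 10.3.3 defines a second set, for non-target disease, with the same one-cycle and re-evaluation conditions.
- **Analysis (10.4.3).** "The overall response rate (ORR) of up to 6 cycles of VIPOR in PCNSL and SCNSL will be reported along with a 95% confidence interval". CR is handled the same way. Neither item names a population or points to 10.3.2, and the interval method is not given.
- **Endpoint table (10.1).** "ORR = CR+PR- assessed after cycles 3 and 6". No denominator appears here either.
- **Primary endpoint (10.3).** "Any participants who received at least one dose of any study drugs will be evaluated for success".
- **Arm 1 (10.2).** Of the four VIPOR-Nivo participants: "These participants will not be included in the analysis of the primary endpoint but will be evaluated for toxicity and survival outcomes". Response is not mentioned for them.
- **Assessments (3.4.3.1).** Restaging follows cycles 1, 3 and 6. "If a participant stops treatment for any reason other than disease progression before completion of 6 cycles, response assessments should continue".
- **Further exclusion (6.3).** Participants whose tumor mass was completely resected are not evaluable for response.

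**The concern.** Under 10.3.2, membership of the response set depends on what happens after treatment starts. Two kinds of dosed participant fall out: those who leave in cycle 1 through death, toxicity or withdrawal without objective progression, and those whose disease is never re-evaluated, whenever they are lost. No section counts them as non-responders. Most will have had no response, so removing them usually raises the rate. The interval around that rate would also describe a selected subset and not the treated group. With about 10 participants, each exclusion moves the estimate by several percentage points. The plan already uses an all-dosed rule for its primary endpoint but does not carry it over to response.

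**Working it through.** **The plan's own figure.** Section 10.2 requires at least 7 successes in 10. The exact binomial gives P(X ≥ 7 | 0.5) = (120 + 45 + 10 + 1)/1024 = 0.1719 and P(X ≥ 7 | 0.8) = 0.8791, matching the stated 17.2% and 87.9%. These concern the primary endpoint and are not in dispute. The plan states no sample size, power or precision for ORR or CR.

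**Who is in and who is out.**

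| Dosed participant with disease at baseline | 10.3.2 set |
|---|---|
| Objective progression before the end of cycle 1 | in, by the note |
| Receives one cycle and is re-evaluated, then stops | in |
| Dies in cycle 1 without documented progression | out |
| Stops in cycle 1 for toxicity or withdrawal, no progression | out, even if scanned later, unless what was given counts as one cycle (not defined) |
| Receives one cycle but is never re-evaluated | out |

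**Inputs for the size.** N = 10 treated in Arm 2 (10.2), all assumed to have baseline disease that was not completely resected. The documents give neither a response rate nor an early-loss rate, so responders r = 3 to 7 and exclusions k = 0 to 2 are assumptions. Intervals are Clopper-Pearson, also an assumption.

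**Formulas.**
- k excluded non-responders: shift = r/(10 − k) − r/10. This is 0 for k = 0, r/90 for k = 1 and r/40 for k = 2.
- One excluded responder: shift = (r − 1)/9 − r/10 = (r − 10)/90.

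**Results, in percentage points.**

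| r | k = 1 non-responder | k = 2 non-responders | 1 responder excluded |
|---|---|---|---|
| 3 | +3.3 | +7.5 | −7.8 |
| 4 | +4.4 | +10.0 | −6.7 |
| 5 | +5.6 | +12.5 | −5.6 |
| 6 | +6.7 | +15.0 | −4.4 |
| 7 | +7.8 | +17.5 | −3.3 |

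**Example with r = 6.**
- All treated: 6/10 = 60.0% (95% CI 26.2 to 87.8).
- One non-responder excluded: 6/9 = 66.7% (29.9 to 92.5).
- Two non-responders excluded: 6/8 = 75.0% (34.9 to 96.8).
- One responder excluded: 5/9 = 55.6% (21.2 to 86.3).

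The interval around 6/10 is 87.8 − 26.2 = 61.6 points wide, more than any shift in the table.

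**Larger N.** Section 10.2.1 allows for 2 inevaluable participants. If both were dosed and then dropped as non-responders, 6/12 = 50.0% (21.1 to 78.9) would be reported as 6/10 = 60.0% (26.2 to 87.8).

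**The case against.** The strongest reply is that 10.3.2 is a prespecified response population under the heading for analysis populations, and that a response-evaluable set is an ordinary choice in a small pilot. On that view 10.4.3 lacks only a cross-reference. This is partly right. A reader might infer that the plan has no response denominator at all; the documents do not support that, because 10.3.2 is the natural one. But adding the cross-reference would confirm the exclusion, not remove it.

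A reader might also infer that early failures in general are dropped. They are not. Cycle 1 progressors are kept, and assessments continue after other early stops. Section 3.4.3.2 requires a full work-up at suspected progression and also covers this case: "In the event that disease progression is not confirmed, yet a decision is made to initiate a new anti-cancer treatment for any reason". The oral agents end on day 14 of a 21-day cycle, so someone who stops after that and is rescanned has arguably received the cycle. The gap is therefore narrow, but those who die or stop without objective progression remain in it.

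Nor are early toxicity and death hidden. Stopping for toxicity before completing two cycles fails the primary endpoint, toxicity is tabulated from first treatment, and deaths are PFS and OS events. The report should also show how many participants were dosed. This limits the harm; it does not make the response rate describe the treated group.

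Finally, the size rests wholly on assumed counts, and the shift can be zero or negative. That stands.

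**Conclusion.** The point holds and is minor. Followed as written, 10.3.2 can give ORR and CR rates that differ from those among all treated participants. The usual direction is upward. It reverses if someone who stopped in cycle 1 and was excluded later responds, which is possible because assessments continue. For 10 treated and 3 to 7 responders, one excluded non-responder adds 3.3 to 7.8 points and two add 7.5 to 17.5; no exclusions means no difference. These are illustrations on assumed counts, not forecasts.

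A reader might go further and infer that the trial's conclusion on safety and feasibility is biased. The documents do not support that: the success criterion uses everyone dosed, section 6.3 says response is not the primary endpoint, and ORR and CR carry no threshold or decision rule. What is affected is the meaning of two secondary estimates.

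**What to change.** - In 10.4.3, report ORR and CR with all Arm 2 participants who received any dose and had measurable or evaluable disease at baseline as the denominator. Keep the complete-resection exclusion of 6.3, and count participants with no documented response as non-responders. Naming Arm 2 also makes clear that the four VIPOR-Nivo participants are outside these rates.
- Report the 10.3.2 set as a supporting analysis, with the number of dosed participants it excludes.
- Do not restrict which scans count as part of this change. The endpoint table places response after cycles 3 and 6, but 3.4.3.1 also restages after cycle 1, 6.3.7 takes best response from the start of treatment, and 6.3.8 starts DOR at the first recorded CR or PR. A participant with a PR after cycle 1 who progresses before the next scan could be an ORR non-responder and still have a DOR. Reconcile these sections separately, so that ORR and DOR use the same responders.

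The denominator change costs a short text amendment and one table line, with no new procedure or data. Its downside is that the reported rate may be lower. Making it before analysis avoids choosing the denominator after the results are known.
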